End-of-Study for Patient	The end of study for a patient is when the patient has completed the required post-treatment study visits or has discontinued from the study.
Enrolled Patient	Individual who has signed the Informed Consent Form.
Elimination of Saphenous Vein Reflux	Vein closure and/or vein competence of the treatment section (TS) of the selected saphenous vein, as demonstrated by duplex ultrasound at Week 12 post treatment (Visit 6)
Follow-up Period	From the day following Day of Treatment (Visit 3) to completion of the Week 1, 6 and 12 (Visits 4, 5 and 6) post-treatment follow-up visits
HASTI	H eaviness, A chiness, S welling, T hrobbing, I tching symptom from VEINES-QOL/Sym questionnaire
Institutional Review Board (IRB)	A type of committee used in research in the United States that has been formally designated to approve, monitor, and review biomedical and behavioral research involving humans
Regulatory Agency	USA Food and Drug Administration (FDA)
Saphenous Vein Segment	A segment of saphenous vein with no deep venous junction
Screening Period	After reviewing and signing the Informed Consent Form (ICF) for participation in the study, an individual will be screened for eligibility to participate in study during Screening (Visit 1), Baseline (Visit 2), Day of Treatment (Visit 3).
Sponsor	Vascular Insights, LLC

Term	Definition
Start-of-Study	Study starts when first patient signs the ICF (Visit 1).
Study Drug	Sodium Tetradecyl Sulfate (STS) 1% and 3%
Study Drug Delivery System	ClariVein infusion catheter system
Study Product	ClariVein RES (Sodium Tetradecyl Sulfate delivered via the ClariVein infusion catheter system)
VICARES Clinical Study Procedure Manual	A manual provided to the Investigational Sites that include instruction for device operation, study drug and delivery device preparation, and ultrasound assessments for the ClariVein RES.
Study Treatment	The study treatment, is the endovenous administration of either 1% or 3% STS delivered intravenously via the ClariVein, with a maximum STS volume of 10 mL per single treatment procedure.
Suspected Adverse Event	Any adverse event (AE) for which there is a reasonable possibility that the study product caused the AE. For the purposes of IND safety reporting, "reasonable possibility" means there is evidence to suggest a causal relationship between the investigational product and the AE.

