3. STUDY OBJECTIVE

3.1. Objectives and Endpoints

Objectives and related endpoints are described in [Table 1](#).

[figure not shown]
Table 1: Study Endpoints

Primary Endpoint Improvement in patient reported symptoms using, HASTI symptoms (heaviness, aching, swelling, throbbing and itching) from the VEINES-QOL/Sym Questionnaire at post treatment Week 12 compared to Baseline.	Section 11.3
Secondary Endpoint Elimination of saphenous vein reflux post treatment as demonstrated by duplex ultrasound at Week 12 post treatment.	Section 11.3.1
Tertiary Endpoints Assessment of patient improvement at Week 12 post treatment as compared to the Baseline using the following scales: 
• Clinical-Etiology-Anatomy-Pathophysiology (CEAP) Classification• European Quality of Life Scale (EQ-5D-5L)• Revised Venous Clinical Severity Score (rVCSS)• Wong Baker Visual Analog Pain Scale (VAS scale)	Section 11.4
Exploratory Assessment in patient reported symptoms	Section 11.5
Week 1 VEINES-QOL-SYM (Questions 1 through 8)	
Week 6 VEINES-QOL-SYM (Questions 1 through 8)	
Week 12 VEINES-QOL/Sym (Question 1, excluding HASTI, through Question 8)	

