8.2.2. Elimination of Saphenous Vein Reflux

Elimination of saphenous vein reflux at Week 12 post treatment, as demonstrated by duplex ultrasound based on vein closure and/or vein competency.

Vein Closure is defined as no discrete open segment of vein $> 5\text{cm}$ in length within the treatment section of the selected saphenous vein as assessed by duplex ultrasound.

Vein Competency is defined as absence of retrograde flow $> 500\text{ ms}$ (0.5 sec) within the treatment section of the selected saphenous vein as assessed by duplex ultrasound.

The endpoint is achieved when ultrasound images demonstrate vein closure and/or vein competency as read by an independent vascular core lab.

Refer to the [Appendix C](#) VICARES Clinical Study Procedure Manual for details.

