11.3.1. Secondary Efficacy Endpoint

Elimination of saphenous vein reflux at Week 12 post-treatment as demonstrated by duplex ultrasound.

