11.8. Analysis of Other Efficacy Endpoints

The primary analysis for each endpoint will use LOCF methodology for the imputation of missing data.

Continuous endpoints will be summarized using descriptive statistics and will be analyzed using a one-sample t-test to test the null hypothesis that the mean change from baseline equals 0.

The secondary efficacy endpoint, the elimination of saphenous vein reflux at Week 12 post-treatment, will be summarized for both treatments combined using the count and percentage, together with a 95% Wilson (score) confidence interval for the proportion.

To evaluate a dose-response relationship, two analyses will be performed for each endpoint. First, the analyses performed for both treatments combined will be repeated for each treatment group separately. Secondly, for continuous endpoints, an ANCOVA will be performed to compare the change from baseline for STS 1% versus STS 3% with treatment as the class variable and with baseline score as the covariate. For vein closure rate, the treatment difference for STS 1% versus STS 3% for the proportion will be assessed by a chi-square test together with a 95% Wilson (score) confidence interval for the treatment difference.

For each continuous endpoint, the change from baseline to each scheduled visit will be analyzed in the same manner as the Week 12 assessment. Both LOCF and observed cases analyses will be performed.

The correlation between Week 12 efficacy endpoints will be explored using a Spearman correlation coefficient for pairs of quantitative variables, and Kendal's tau for the correlation of the elimination of saphenous vein reflux (yes, no) with quantitative variables.

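### Section 11.8 assigns the 1% versus 3% chi-square test and Wilson interval to vein closure rate, not to the secondary endpoint, elimination of saphenous vein reflux

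*Combined protocol and SAP*

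**What the plan says.** Table 1 in section 3.1 gives the secondary endpoint as "Elimination of saphenous vein reflux post treatment as demonstrated by duplex ultrasound at Week 12 post treatment", and section 11.3.1 repeats it: "Elimination of saphenous vein reflux at Week 12 post-treatment as demonstrated by duplex ultrasound". The List of Terms and Definitions explains it as "Vein closure and/or vein competence of the treatment section (TS) of the selected saphenous vein". Section 8.2.2 sets the success rule: "The endpoint is achieved when ultrasound images demonstrate vein closure and/or vein competency as read by an independent vascular core lab". Section 5.1.3.1 of the Procedure Manual (Appendix C) agrees.

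The two components are defined separately in the List of Terms, in section 8.2.2 and in Appendix C 5.1.3.1. Closure means no open stretch longer than 5 cm in the treatment section. Competence means no retrograde flow longer than 500 ms there.

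Section 11.8 handles the endpoint in four places:

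- Pooled summary: "The secondary efficacy endpoint, the elimination of saphenous vein reflux at Week 12 post-treatment, will be summarized for both treatments combined", with a 95% Wilson interval.
- Dose response: "To evaluate a dose-response relationship, two analyses will be performed for each endpoint". The first of the two repeats the pooled analysis within each arm.
- Between-dose comparison of a proportion: "For vein closure rate, the treatment difference for STS 1% versus STS 3% for the proportion will be assessed by a chi-square test", with a 95% Wilson interval for the difference.
- Correlations: Kendall's "tau for the correlation of the elimination of saphenous vein reflux (yes, no) with quantitative variables".

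Only the third item names closure.

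**The concern.** Closure rate is one of two routes to success on the secondary endpoint. It does not appear among the primary, secondary, tertiary or exploratory endpoints in Table 1 or sections 11.3 to 11.5. If the sentence is programmed as written, the randomised dose comparison of the ultrasound outcome is made on an undeclared variable. The declared secondary endpoint then gets per-arm rates but no test and no interval for the difference.

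Two programmers could produce different tables from this text and each could defend the choice. If the question is settled only after the blind is broken, the choice is open to criticism. Dose is the only randomised contrast in the trial, and this is its only secondary endpoint.

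**Working it through.** **1. Plan's own figure.** The documents give no expected rate, difference or power for the ultrasound endpoint. The only power statement (section 11.6) concerns the one-sample t-test on HASTI change. The standardised change is 5.44/3.52 = 1.545, which gives power above 99.9% at n = 25, so the stated minimum of 99% at both 25 and 50 is reproduced. It has no bearing on this point.

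**2. Are the two terms interchangeable?** Cross-classify a treated vein at Week 12:

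| Open segment > 5 cm | Retrograde flow > 500 ms | Closure | Elimination |
|---|---|---|---|
| No | No | success | success |
| No | Yes | success | success |
| Yes | No | **not closed** | **success** |
| Yes | Yes | not closed | failure |

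They differ in the third row only. Appendix C expects that case: section 5.1.1.1 has open segments over 5 cm checked for reflux, and section 5.1.3.2 calls a vein a failure only if such a segment shows retrograde flow over 500 ms. Every closed vein is also an elimination success, so in each arm the closure rate is at most the elimination rate.

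**3. Effect on the dose difference.** Let k1 and k3 be the numbers of open-but-competent veins in the 1% and 3% arms, with 25 patients per arm (section 11.6). Then

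closure difference (1% − 3%) = elimination difference (1% − 3%) − (k1 − k3)/25.

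One patient is 1/25 = 4 points. If k1 = k3 the difference is unchanged. An excess of one to three in one arm (assumed) shifts it by 4 to 3/25 = 12 points.

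**4. Illustration with assumed counts.** The method is a Pearson chi-square without continuity correction and the Newcombe interval built from the Wilson limits (l, u) of each arm: lower = d − √[(p1 − l1)² + (u2 − p2)²], upper = d + √[(u1 − p1)² + (p2 − l2)²].

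- Elimination 22/25 v 22/25: difference 0, interval −19.6 to 19.6 points, p = 1.00.
- Three successes in one arm are open but competent, so closure is 22/25 v 19/25. The Wilson limits are 70.0 to 95.8 and 56.6 to 88.5. The difference is 12 points, interval −9.9 to 32.9. Chi-square = 50 × (22×6 − 3×19)² / (25×25×41×9) = 1.22, p = 0.27.

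**5. When would significance change?** Take equal elimination in both arms and place all discordant veins in one arm. The fewest needed for the closure test to reach p ≤ 0.05 are:

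| Elimination per arm | Discordant veins needed | Closure comparison | p |
|---|---|---|---|
| 20/25 | 7 | 20 v 13 | 0.037 |
| 21/25 | 7 | 21 v 14 | 0.031 |
| 22/25 | 6 | 22 v 16 | 0.047 |
| 23/25 | 6 | 23 v 17 | 0.034 |
| 24/25 | 5 | 24 v 19 | 0.042 |

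One fewer misses in every row (p = 0.059 to 0.088).

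Elimination need not be equal. With assumed elimination of 24/25 v 22/25, the difference is 8 points (−9.4 to 26.3), p = 0.30. If 1 and 5 of those successes respectively are open but competent, closure is 23/25 v 17/25, 24 points (1.5 to 44.4), p = 0.034.

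**The case against.** The strongest reply is that section 11.8 resolves the matter itself. It announces dose-response analyses for every endpoint, then gives one method for continuous endpoints and one for a proportion. The only endpoint it summarises as a proportion is elimination of reflux. Closure rate is not a listed endpoint, so the coherent reading is that it is shorthand. Appendix C is similarly loose, since its section headed Closure includes checking for reflux. Elimination rates with Wilson intervals would be reported per arm under either reading, so anyone could work out the difference. The comparison is supportive, in a 50-patient pilot whose primary test pools the arms. The counts above are all assumed. At 24 v 19 the expected number of failures is 3.5 per arm, where an uncorrected chi-square is unreliable.

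Most of this stands. Shorthand is the likely explanation, the sponsor probably intends the right variable, and the practical effect is likely to be modest. Nor is anything wrong with the choice of a chi-square test or a score interval. The 1% versus 3% ANCOVA comparisons for HASTI and the other continuous endpoints are also specified properly, so the gap is confined to the binary ultrasound outcome. What does not stand is that the text is harmless as written. The shorthand is a term to which the protocol gives its own, narrower definition, and the same section uses the correct name before and after it.

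**Conclusion.** The point holds. As written, the between-dose test and interval for the ultrasound outcome apply to vein closure rate, and the secondary endpoint lacks the comparison that section 11.8 promises. This should be corrected.

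The size depends on how many veins are open but competent at Week 12, which the documents do not indicate. Each moves its arm's rate by 4 points, and only an imbalance between arms changes the dose difference. When elimination is equal at 20/25 to 24/25, it takes five to seven discordant veins, all in one arm, to create a nominally significant closure difference. The realistic consequence is therefore a wrong estimate or a wrong label rather than a changed significance result. These figures assume 25 evaluable patients per arm, an uncorrected chi-square and the Newcombe form of the score interval. The HASTI primary analysis, its power and the per-arm elimination rates are not affected.

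**What to change.** In the 1% versus 3% sentence of section 11.8, replace vein closure rate with elimination of saphenous vein reflux, before the blind is broken. If the sponsor does want a between-dose comparison of closure, list it as an additional analysis alongside the elimination comparison. Closure and competence could also be shown as descriptive component rows where both readings exist, but this is optional. The 5 cm closure tolerance is defined consistently and needs no change.

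The cost is one phrase: no extra scans, visits, readers or patients, and no change to any endpoint definition.

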11.9. Analysis of the Safety Endpoints

Safety will be assessed based on adverse events (including selected events of interest), clinical laboratory tests, physical examination, vital signs, and concomitant medications. Safety data will be summarized by treatment group and overall. No statistical testing will be performed for safety data.

AEs will be coded using Medical Dictionary for Regulatory Activities (MedDRA). Treatment-emergent events are those adverse events that begin or worsen after initiation of the treatment procedure. The number and percentage of patients reporting treatment-emergent adverse events will be summarized by MedDRA System Organ Class (SOC) and Preferred Term. Treatment-emergent adverse events will be further summarized by severity and relationship to the treatment procedure.

Physical examination data will be listed per patient. No summaries will be provided.

Vitals signs data will be summarized by descriptive statistics for baseline, each post-treatment visit, and the change from baseline to each post-treatment visit.

All prior and concomitant medications will be coded using the World Health Organization Drug Dictionary. Concomitant medications are medications taken on or after the treatment day, regardless of when they were started. Prior medications are medications taken before the treatment day, regardless of when they ended. The number and percentage of patients using

concomitant medications will be summarized by Anatomical Therapeutic Chemical (ATC) 3 classification and preferred name.

Overall safety assessment will include evaluation of the following specific events:

- Neurological events including: stroke, TIA, visual symptoms, migraines
- Venous Thromboembolic Events (VTE) in the treated leg
- Post-treatment local effects including hyperpigmentation, granuloma formation, ulceration in the treated leg
- Thrombus formation in deep veins (e.g., femoral vein) in the treated leg
- Post-ablation superficial thrombus extension (PASTE) in the treated leg
- Local and systemic allergic reactions, including anaphylaxis

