10.11. Relationship to Study Treatment

The assessment of study drug relationship to each AE will be reported on the appropriate source document (and SAE form, in the event of an SAE) by the Investigator (or designated sub-Investigator) per his/her best clinical judgment. The criteria listed in Table 4 should be used to guide this assessment. Please note that not all criteria must be present to be indicative of a particular drug relationship. All study drugs are considered “test drugs” for the purposes of the definitions listed in Table 4.

Table 4: Adverse Event Causality Guidelines

Relationship	Criteria for Assessment
Definitely related	There is evidence of exposure to the test drug; and 
- The temporal sequence of the AE onset relative to administration of the test drug is reasonable.- The AE is more likely explained by the test drug than by another cause.- Dechallenge (if performed) is positive.- Rechallenge (if feasible) is positive.- The AE shows a pattern consistent with previous knowledge of the test drug or test drug class.
Probably related	There is evidence of exposure to the test drug; and 
- The temporal sequence of the AE onset relative to administration of the test drug is reasonable.- The AE is more likely explained by the test drug than by another cause.- Dechallenge (if performed) is positive.
Possibly related	There is evidence of exposure to the test drug; and 
- the temporal sequence of the AE onset relative to the administration of the test drug is reasonable; and- the AE could have been due to another equally likely cause.
Not related	There is evidence of exposure to the test drug; and 
- there is another more likely cause of the AE,- dechallenge (if performed) is negative or ambiguous,- rechallenge (if performed) is negative or ambiguous. 
The patient did not receive the test drug; or
 
Temporal sequence of the AE onset relative to administration of the test drug is not reasonable; or
 
There is another obvious cause of the AE.

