10.13. Monitoring and Recording of Adverse Events

AE data collection will begin after a patient signs the ICF and will continue until completion of their Week 12 post-treatment follow-up visit (Visit 6). Any AE or SAE having an onset after the completion of Visit 6 (end of the study visit) will not be collected or reported unless the Investigator feels that the event may be related to the study drug.

Patients will be instructed by the Investigator or designee to report the occurrence of any AE. All volunteered, elicited, and observed AEs are to be recorded on the AE eCRFs.

The Investigator will assess all AEs regarding any causal relationship to the study drug ([Section 10.11](#)), the intensity (severity) of the event, action taken, and patient outcome.

The following criteria will be used to guide the assessment of intensity (severity):

- **Mild:** An adverse event that is asymptomatic or barely noticeable to the patient; not interfering with patient's daily activity performance or functioning; generally, not requiring alteration or cessation of study drug administration; and/or ordinarily not needing therapeutic intervention
- **Moderate:** An adverse event of sufficient severity as to possibly make the patient moderately uncomfortable; some interference with the patient's daily activity performance or functioning; generally, not impairing the patient's ability to continue in the study; and/or possibly needing therapeutic intervention.
- **Severe:** An adverse event generally causing severe discomfort; major interference with the patient's daily activity performance or functioning; generally requiring alteration or cessation of study drug administration; life-threatening; resulting in

significant disability or incapacity; and/or generally requiring therapeutic intervention.

All AEs will be followed until resolution, until deemed stable by the Investigator, or until the patient is deemed by the Investigator to be lost to follow-up.

For clinical study safety reporting purposes, the most recent version of the Investigator's Brochure (IB) will be used as the reference document to designate event expectedness. An AE is considered unexpected if the AE is not listed in the current IB or is not listed in the IB at the specificity or severity observed.

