10.14. Reporting of Serious Adverse Events

Serious AEs (SAE) which occur from the time the patient provides informed consent to the end of the study, require immediate notification to VI's Compliance Department or its designated representative. All SAEs must be reported within 24 hours of discovery, by faxing or emailing the report.

The written report should be submitted on the SAE form provided for this purpose. The report must include the Investigator's opinion as to whether the event is study drug-related. If this relationship is determined to be possibly, probably, or definitely related to study drug, evidence to support this assessment must also be provided.

Documentation regarding the adverse event should be made as to the nature, date of onset, end date, severity, and relationship to the investigational product, action(s) taken, seriousness, and outcome of any sign or symptom observed by the Investigator or reported by the patient upon direct questioning.

Expected outcomes related to the procedure should not be recorded as adverse events.

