4.1.4.4. Activating the Rotatable Dispersion Wire

1. Prior to activating rotation of the dispersion wire confirm the:
 - a. position of the dispersion wire tip within the Treatment Section utilizing ultrasound imaging guidance
 - b. dispersion tip is **not** within the vascular access device
 - c. speed selection is at 3500 RPM
 - d. patient is informed they will feel a slight vibration along the treated vein.
2. Activate rotation of the dispersion wire by depressing the trigger.

Caution: Only activate rotation of the dispersion wire while **simultaneously** slowly withdrawing (pulling back) the catheter assembly.

3. During the first 1 cm of pull back, activate the dispersion wire rotation, but do not infuse any fluid. For the remainder of the procedure, pull back with **simultaneous** dispersion wire rotation and infusion of fluid.
4. After the first 1 cm of pull back with wire rotation alone (without infusion of any fluid), slowly withdraw the device through the treatment area while simultaneously infusing the STS.
 - a. The procedure is carried out using both hands moving simultaneously.

- b. Depress the syringe plunger with the thumb of the same hand that is holding the MDU (**Figure 6**).
- c. Perform a controlled pull back (withdrawal) of approximately 6 – 7 sec / cm.
- d. While the Dispersion Wire is rotating, hold the MDU with one hand while using the other hand to gently grasp the catheter sheath between your thumb and index finger proximal to the access site; pull back slowly and smoothly with 2 hands ensuring the ClariVein® catheter sheath does not kink or become damaged.
- e. Ensure the orientation of the MDU is in straight alignment and pointed towards the Catheter Assembly. The catheter must be kept straight between the Access Site and the point being grasped by the physician.

Note: For veins with diameters ≥ 10 mm, slight compression with the ultrasound probe is recommended. If the patient feels any discomfort, compression should be abandoned.

Caution: Do not forcefully compress the vein at the location of the rotating (spinning) dispersion wire tip either manually or with an ultrasound probe during the procedure. It is not recommended to continuously follow the rotating (spinning) dispersion wire tip with the ultrasound probe. Doing so may result in the dispersion wire becoming ensnared with the vein, damage to the device, and/or cause patient discomfort.

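### Section 11.9 tabulates adverse events by relationship to the treatment procedure, but sites are told to grade causality mainly against STS and never against the procedure

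*Combined protocol and SAP*

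**What the plan says.** Section 11.9 (Analysis of the Safety Endpoints) states: "Treatment-emergent adverse events will be further summarized by severity and relationship to the treatment procedure".

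The sections that tell sites what to grade use other targets:

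- **Section 10.11:** "The assessment of study drug relationship to each AE will be reported on the appropriate source document". Every category of Table 4 is worded in terms of the test drug. The grounds for *Not related* include "there is another more likely cause of the AE" and, separately, "There is another obvious cause of the AE".
- **Section 10.13:** the investigator judges all AEs for a causal link to the study drug. Events that begin after Visit 6 "will not be collected or reported unless the Investigator feels that the event may be related to the study drug".
- **Section 10.14, SAE report:** "The report must include the Investigator's opinion as to whether the event is study drug-related". A later sentence in the same section asks for relationship to the investigational product instead.
- **List of Terms:** a suspected adverse event is "Any adverse event (AE) for which there is a reasonable possibility that the study product caused the AE". The same list defines study drug as STS 1% and 3%, lists the ClariVein separately as the delivery system, and defines study product as the two together.

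The Procedure Manual (Appendix C, 4.1.4.4) recognises mechanical hazards. It warns against forceful compression at the spinning tip and against following the tip continuously with the probe: "Doing so may result in the dispersion wire becoming ensnared with the vein, damage to the device, and/or cause patient discomfort".

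**The concern.** The product under test is a drug delivered by a rotating-wire catheter, so an adverse event may come from the sclerosant, the device or the access procedure. The analysis text reports one of these attributions, and the collection text mostly asks for another. Whoever programs the 11.9 table must either relabel drug grades as procedure grades or find a variable that the protocol does not describe.

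Relabelling could place catheter or access injuries in the unrelated row of a table whose title says it shows relationship to the procedure. Safety data receive no statistical testing (11.9) and no Data Monitoring Committee is planned (12.4), so the descriptive tables carry the safety reading. Attribution is also best made by the investigator when the event occurs, and it is hard to reconstruct after database lock.

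**Working it through.** No calculation applies. The check sets the causality passages side by side and then follows example events through Table 4.

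**Step 1. Which target does each passage name?**

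| Place | Role | Target |
|---|---|---|
| 10.11 text and Table 4 | Grading instruction and the only scale | Study (test) drug |
| 10.13 | Instruction for all AEs; late-event rule | Study drug |
| 10.14, SAE report | Investigator opinion | Study drug |
| 10.14, documentation sentence | What to document | Investigational product |
| List of Terms, suspected adverse event | Definition | Study product |
| 10.7.1, suspected adverse reaction | Definition | Drug |
| 10.6 | General reporting statement | ClariVein RES investigational product |
| 8.1 | List of AE attributes | Relatedness, no target given |
| 10.7.2 | Device reporting definitions | No causality grading |
| 11.9 | Analysis | Treatment procedure |

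Three operational instructions name the drug. One documentation sentence names the combined product. None names the procedure, which appears as a causality target only in the analysis section.

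**Step 2. Is drug merely shorthand for the combination?** The List of Terms gives study drug, delivery system and study product separate entries. As defined, a study-drug grade is a grade for STS.

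**Step 3. Follow three events through Table 4.**

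- *Clearly mechanical event, such as the wire catching in the vein.* The device is the more likely and obvious cause, so the event meets the criteria for *Not related*. Timing can lead to the same grade. Appendix C 4.1.4.4 has the first 1 cm of pull-back done with rotation and no infusion, so an injury there precedes any STS. Section 11.9 still counts it as treatment-emergent, because it counts from the start of the procedure.
- *Local event after rotation and infusion together.* From the second centimetre the two are simultaneous, and often neither cause is clearly more likely. Table 4 grades an equally likely alternative as *Possibly related*, so this event is not lost.
- *Event beginning after Visit 6 and attributed only to the catheter or access.* The late-event exception in 10.13 depends on the study drug. Read literally, the event is not collected.

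**Step 4. What does this do to the tables?** The summary by System Organ Class and Preferred Term uses no causality grade and is unchanged. The breakdown by relationship is the part left without a defined input.

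**The case against.** The strongest reply is that this is loose terminology around one relatedness item. Section 10.11 is headed with study treatment, which the List of Terms defines as STS given through the ClariVein. Section 4.2.2 speaks of a single treatment procedure with ClariVein RES, and 10.14 asks once about the investigational product. On that view, procedure in 11.9 means the whole treatment. This has force: the text is inconsistent, not uniformly drug-only. But the body of 10.11 and all of Table 4 narrow the heading to the drug, and neither study treatment nor investigational product has a scale of its own.

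Four stronger readings are tempting, and the documents do not support them:

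- **That the table cannot be produced.** The AE eCRF and SAE form are not in the documents and may hold a product or procedure field. What can be said is that the protocol defines no source variable.
- **That device events will be graded *Not related*.** Table 4 guides clinical judgement, does not require every criterion, and grades an equally likely other cause as *Possibly related*. Only events with a clearly more likely mechanical or access cause are exposed.
- **That the 1% versus 3% safety comparison becomes unreadable.** The arms are randomised, blinded and share the device and procedure. Comparing all treatment-emergent events by arm already isolates STS strength without individual attribution.
- **That each misgraded event moves an arm's related-event rate by 1/25 = 4 percentage points.** Section 11.9 counts patients, so this holds only if the event was that patient's sole related one. No event rate is given, and a shared device gives no reason to expect misgrading to differ by arm.

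The late-event gap is probably small in practice. The catheter is removed on Day 1, and nothing in the documents suggests that device events first appearing after Week 12 are expected.

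**Conclusion.** The concern holds as a mismatch between what is collected and what is analysed. Causality is graded mainly against STS, once against the combined product, and never against the procedure that 11.9 tabulates. If drug grades are used for that summary, clearly catheter- or access-caused events can appear as *Not related*, and the 10.13 wording omits late events attributed only to device or procedure.

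The damage is confined to the relatedness breakdown and late-event capture. Its size cannot be estimated, because the documents give no rate of device or procedure events. The conclusion assumes that sites follow Table 4 and the defined terms as written, and that the unseen forms add no separate procedure item. If they do add one, the protocol still lacks a definition and scale for it. The point is worth correcting before sites begin grading, but it does not threaten the between-arm safety comparison.

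**What to change.** 1. In 10.11 and on the AE and SAE forms, record relationship to STS, to the ClariVein device and to the procedure as three separate items, each on the existing Table 4 categories with the wording adapted to the item.
2. In 11.9, summarise treatment-emergent events by each of the three items and by any of them.
3. In the 10.13 late-event rule and the 10.14 SAE opinion, reconcile the causality wording with the study-product definition in the List of Terms, so that device and procedure are covered.
4. State which outcomes 10.14 means when it says that expected results of the procedure are not recorded as AEs. Without this, the procedure item would be incomplete from the start.

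Using one causality term throughout would be cheaper and would remove the contradiction, but it would not separate drug from device or procedure.

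Cost: about two more causality fields per AE, assuming the current form has one (it is not in the documents), short wording changes in four sections, and extra columns in one descriptive table. No clinical rule changes.
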